APPENDIX B

REQUISITE DOCUMENTS FOR APPROVAL OF STUDY SITE

REQUISITE DOCUMENTS FOR APPROVAL OF STUDY SITE

Investigational product will be provided to the investigators after they have submitted the following documents to the Sponsor or Study Monitor (if applicable):

- Signed statement of Investigator (if required by the regulatory agency)
- Institutional review board or IEC composition
- Document indicating IRB or IEC approval of the final protocol and amendment(s) if applicable (to include name, address, and chairperson of the IRB or IEC)
- Document indicating IRB or IEC approval of the final and revised ICF if applicable (to include name, address, and chairperson of the IRB or IEC)
- Blank copy of the IRB or IEC-approved final and revised ICF
- Signed Investigator's study agreement and confidentiality disclosure agreement
- Laboratory certification or accreditation and normal ranges for tests that are performed in the laboratory for study assessments
- Curricula vitae for the Investigator and subinvestigator(s) listed on the Form FDA 1572 of the study.
- Financial disclosure for the Investigator and subinvestigator(s) listed on the Form FDA 1572 of the study.

APPENDIX C

RESPONSIBILITIES AND OBLIGATIONS OF INVESTIGATORS AND SPONSORS

RESPONSIBILITIES AND OBLIGATIONS OF INVESTIGATORS AND SPONSORS

For non-treatment protocols (e.g., separate follow-up protocol, observational protocol), some of the following may not be applicable.

1.0 SPONSOR

The following sections describe the responsibilities and obligation of the Sponsor or designee.

1.1 Conduct a site selection visit or study initiation visit to:

- 1.1.1 Establish the acceptability of the facility and record the visit in a written report (i.e., memorandum or form).
- 1.1.2 Discuss with the Investigator the proposed study and supply him or her with draft eCRFs, the Investigator's Brochure, and the draft protocol for his or her review and approval.
- 1.1.3 Discuss with the Investigator the regulatory requirements with respect to informed consent, IRB/IEC approval of the trial, the protocol, protocol amendments, and changes to the ICF.
- 1.1.4 Discuss with the Investigator the timing of interim and final reports to the Study Monitor and his or her obligation to supply the Study Monitor with copies of all study-related documents (including IRB or IEC approval, IRB or IEC charter or equivalent, membership and qualifications, protocol amendments, ICFs, and consent changes), eCRFs, eCRF changes, and all pertinent correspondence to and from the IRB or IEC.

1.2 Conduct periodic on-site visit(s) to:

- 1.2.1 Ensure adherence to the protocol.
- 1.2.2 Review eCRFs and source documents for accuracy and completeness of information.

Clinical Protocol

- 1.2.3 Examine pharmacy records for documentation of quantity and date of receipt of investigational drug, dispensation and accountability data for product administration to
- 1.2.4 Record and report (summarize) observations on the progress of the trial and continued acceptability of the facilities, and prepare an on-site visit report.

each subject, loss of materials, contamination, and unused supplies.

1.2.5 Review Investigator files for required documents (e.g., protocols; protocol amendments; Investigator's Brochure; SPM; IRB or IEC approval of protocols, amendments, and ICF; IRB or IEC charter and membership; and communications to and from the IRB/IEC and the Study Monitor).

2.0 INVESTIGATOR

2.1 Institutional review board or independent ethics committee

The Investigator must assure the Study Monitor that the IRB or IEC:

- 2.1.1 Meets ICH guidelines as defined in ICH E6 Section 3, IRB/IEC
- 2.1.2 Has the authority delegated by the parent institution and found in the IRB or IEC by-laws, operation guidelines, or charter to approve or disapprove clinical studies and protocols, including the ICF and other documents (e.g., protocol amendments and information to be supplied to subjects concerning informed consent)
- 2.1.3 Complies with proper personnel make-up of the board
- 2.1.4 Convenes meetings using acceptable rules of order for making decisions, recording such decisions, and implementing them
- 2.1.5 Maintains files that contain (a) documentation of its decisions, such as are found in IRB or IEC minutes and correspondence, (b) written guidelines or by-laws governing IRB or IEC functions, (c) protocol, (d) protocol amendments, (e) approved informed consent document and information to be supplied to the subject, and (f) correspondence between the IRB or IEC and Investigator (e.g., consent changes, protocol amendments)

2.2 Informed consent of human subjects

The Investigator must assure the Study Monitor that the ICF for a subject:

- 2.2.1 Meets ICH guidelines as defined in ICH E6, Section 4.8, Informed Consent of Trial subjects
- 2.2.2 Has been approved by the IRB or IEC, including (when required) information to be given to the subject about the trial in which he or she is enrolled
- 2.2.3 Includes the basic elements and any additional elements of informed consent that are appropriate
- Has been signed by both the subject (or the subject's legally acceptable representative), the Investigator, and a witness, and a copy has been given to the subject
- 2.2.5 Is provided, if necessary, to the subject in the "short form" ICF (presented orally to the subject or the subject's legally acceptable representative, with a witness listening) with written information as an alternative
- 2.2.6 Allows for assent to be obtained for minor children as required by the IRB or IEC

2.3 Storage and dispensing of product supplies

The Investigator (or the Investigator's pharmacist) must assure the Study Monitor that:

- 2.3.1 Adequate and accurate written records show receipt and disposition of all product supplies, including dates, serial or lot numbers, quantities received, and each quantity dispensed, administered, or used, with identification of each subject.
- 2.3.2 Purpose and reasons are given in written records for product disposal (e.g., the amount contaminated, broken, or lost) and the quantity that was returned to the Sponsor.

2.4 Case report forms

The Investigator must assure the Study Monitor that:

- 2.4.1 The completed eCRF accurately reflects the hospital records for each subject.
- 2.4.2 The eCRFs and hospital records will be accessible to the Study Monitor during on-site visits.

2.5 Files and records

The Investigator must ensure the quality, integrity, and content of his or her files, which will be subject to audit by the Study Monitor and the appropriate regulatory authority inspectors. The files must contain, as minimum the following:

- Investigator's Brochure
- Investigator's obligations, including the following:
 - 1. 21 Code of Federal Regulations (CFR) Part 312.50, General Responsibilities of Sponsors
 - 2. 21 CFR Part 312.60, General Responsibilities of Investigators
 - 3. 21 CFR Part 50, Protection of Human Subjects
 - 4. 21 CFR Part 56, Institutional Review Boards
 - ICH, E6, Guideline for Good Clinical Practice
- IRB or IEC-approved protocol and protocol amendments
- Blank eCRFs (and amendments to eCRF)
- Study procedures manual and amended pages
- Statement of Investigator forms (copy of signed Form FDA 1572 and a copy of each revised form if required by the regulatory agency) as well as current curricula vitae and bibliography for each Investigator and subinvestigator

- IRB or IEC document, including the following:
 - 1. IRB or IEC charter membership and qualifications of each member
 - 2. IRB or IEC letter of approval of protocol and amendments
 - 3. IRB or IEC letter of approval of ICF and amendments
 - 4. Investigator's annual report to the IRB or IEC
 - 5. IRB or IEC annual re-approval of protocol
 - 6. Reports to IRB or IEC of deaths and serious adverse events (SAEs)
 - 7. Notification to IRB of study completion and Investigator's final report
 - 8. IRB approval of advertisements for subject recruitment (if applicable)
 - All additional correspondence with the IRB/IEC
- IRB/IEC approved informed consent document (all versions) and information to be supplied to the subject
- Study staff signature log
- Subject accountability records, including the following:
 - 1. Subject screening log
 - 2. Medical exceptions log
 - 3. Site status report
 - 4. Subject identification code list
 - 5. Original signed ICF
 - 6. A note stating the location of the eCRFs and data clarification requests
 - Copies of completed eCRF transmittal logs

- Investigation product records, including the following:
 - 1. Receipt, date and quantity, and batch or lot number
 - 2. Disposition dates and quantity administered to each subject
 - 3. Inventory records
 - All correspondence related to the investigational product
- SAE/safety reports
 - 1. Copies of signed SAE reports
 - 2. All SAE correspondence, including MedWatch and Form FDA 3500A
- Biological sample inventory forms and correspondence with the analytical laboratory
- Monitoring activities
 - 1. Monitoring log (should include all visits [i.e., site initiation, periodic, and termination visits])
 - 2. Telephone contact reports
 - 3. Site initiation visit reports
- General Correspondence
 - 1. All correspondence between the Study Monitor, Sponsor, and the site
 - 2. All correspondence between site staff about the protocol

Documents and records must be retained by the Investigator for at least 2 years after the last approval of a marketing application in an ICH region and until there are no pending or contemplated marketing applications in an ICH region or for at least 2 years after the formal discontinuation of clinical development of the investigational product.

1. INTRODUCTION

This document describes the statistical methods and data presentations to be used in the summary and analysis of data from Protocol HTD1801.PCT012. Background information is provided for the overall study design and objectives. The reader is referred to the study protocol and case report forms (CRFs) for details of study conduct and data collection.

1.1. STUDY OVERVIEW

Protocol HTD1801.PCT012 is a Phase 2, multicenter, randomized, double-blind, placebo-controlled, parallel-group, proof-of-concept, and dose-ranging study comparing two doses of investigational product (HTD1801) to placebo. Approximately 117 patients with Nonalcoholic Steatohepatitis (NASH) and Type 2 Diabetes Mellitus (T2DM) will be enrolled as subjects from approximately 15 investigational sites in the United States (US). Upon confirmation of eligibility, subjects will be randomized in a 1:1:1 ratio to one of the following treatment arms:

- **Treatment Arm 1:** HTD1801 500 mg twice daily (BID)
- **Treatment Arm 2:** HTD1801 1000 mg BID
- **Treatment Arm 3:** Placebo BID

Subjects will receive the treatment to which they are randomly assigned for the duration of the 18-week double-blind treatment period. Clinic visits for efficacy assessments and safety monitoring will occur at Week 2, then every 4 weeks throughout the double-blind treatment period. A follow-up safety telephone contact for an assessment of adverse events (AEs) and concomitant medications will take place at least 30 days after the last dose of study drug. An interim analysis will be conducted once a minimum of 51 subjects complete the assessment of the primary efficacy endpoint. An independent Data and Safety Monitoring Board (DSMB) will provide additional safety oversight.

1.2. SCHEDULE OF EVENTS

	SCR	Double-Blind Treatment						ET	Follow-up
		Baseline	WK 2	WK 6	WK 10	WK 14	WK 18		
Visit Day	-28 to -1	0	14	42	70	98	126	-	+30d
Procedure / Window	-	-	±3d	±3d	±3d	±3d	±3d	-	+7d
Administrative Procedures									
Clinic visit	X	X	X	X	X	X	X	X	
Informed consent	X								
Eligibility criteria	X	X ^a							
Demographics	X								
Medical history	X	X ^a							
Randomization		X							
Dispense study drug		X	X	X	X	X			
Return study drug			X	X	X	X	X	X	
Study discharge							X	X	
Telephone contact									X
Clinical Assessments									
Comprehensive physical examination	X						X	X	
Targeted physical examination ^b		X ^a		X		X			
Vital signs	X	X ^a		X		X	X	X	
Weight	X	X ^a	X	X	X	X	X	X	

	SCR	Double-Blind Treatment						ET	Follow-up
		Baseline	WK 2	WK 6	WK 10	WK 14	WK 18		
Visit Day	-28 to -1	0	14	42	70	98	126	-	+30d
Procedure / Window	-	-	±3d	±3d	±3d	±3d	±3d		
Height	X								
ECG	X	X ^a		X		X	X	X	
Laboratory Assessments									
Serum chemistry panel ^c	X	X	X	X	X	X	X	X	
Lipid panel ^c	X	X			X		X	X	
Hematology with differential ^c	X	X			X		X	X	
Coagulation panel ^c	X	X			X		X	X	
HbA1c	X ^d				X		X	X	
HOMA-IR		X					X	X	
HIV and Hepatitis B/C	X								
G6PD	X								
Pregnancy test ^c	X	X ^{a,c}					X	X	
FSH test ^c	X								
Urine drug test	X								
Imaging and Biomarker Assessments									
MRI-PDFP	X ^d						X	X	
Corrected T1 and T2*	X ^d								
Pro-C3		X					X	X	

	SCR	Double-Blind Treatment						ET	Follow-up
		Baseline	WK 2	WK 6	WK 10	WK 14	WK 18		
Visit Day	-28 to -1	0	14	42	70	98	126	-	+30d
Procedure / Window	-	-	±3d	±3d	±3d	±3d	±3d		
ELF test		X					X	X	
Bile acid panel ^c		X			X		X	X	
Safety Assessments									
Adverse event monitoring	X	X ^a	X	X	X	X	X	X	X
Prior and concomitant medications	X	X ^a	X	X	X	X	X	X	X

^a Continued study eligibility confirmed based on updated medical history, targeted physical examination, vital signs, weight, ECG, negative urine pregnancy test (for FOCP), updated prior and concomitant medications, and any adverse events that have occurred since signing informed consent.

^b Targeted physical examination of body systems or organs performed on symptom-driven basis (e.g., adverse events or other findings).

^c See Table 2 of the protocol for analytes tested as part of the serum chemistry, lipid, hematology, and coagulation panels. The serum chemistry panel performed at the Week 2, Week 6, and Week 14 visits only includes testing of ALP, ALT, AST, GGT, total bilirubin, direct bilirubin, and fasting glucose. The Week 10 and Week 18 (or ET) bile acid panel applies only to subjects who have had the Baseline bile acid panel performed.

^d Assessments performed during Screening to confirm study eligibility; results applied as Baseline values.

^e Pregnancy test required for FOCP only; serum pregnancy test performed at Screening and Week 18 (or ET); urine and confirmatory serum pregnancy tests performed at Baseline. FSH test required for postmenopausal females only.

ALP = alkaline phosphatase; ALT = alanine aminotransferase; AST = aspartate aminotransferase; ECG = electrocardiogram; ELF = enhanced liver fibrosis; ET = Early Termination; FOCP = females of child-bearing potential; FSH = follicle-stimulating hormone; G6PD = glucose-6-phosphate dehydrogenase; GGT = gamma-glutamyl transferase; HbA1c = hemoglobin A1c; HIV = human immunodeficiency virus; HOMA-IR = homoeostasis model assessment-estimated insulin resistance; MRI-PDFF = magnetic resonance imaging-estimated proton density fat fraction; SCR = Screening

1.3. GLOSSARY OF ABBREVIATIONS

AE	adverse event
ALP	alkaline phosphatase
ALT	alanine aminotransferase
ANCOVA	analysis of covariance
AST	aspartate aminotransferase
BID	twice daily
BMI	body mass index
CFB	change from baseline
CRF	case report form
CTCAE	Common Terminology Criteria for Adverse Events
DSMB	data and safety monitoring board
ECG	electrocardiogram
ELF	enhanced liver fibrosis
ET	early termination
FSH	follicle-stimulating hormone
G6PD	glucose-6-phosphate dehydrogenase
GGT	gamma-glutamyl transferase
HbA1c	hemoglobin A1c
HOMA-IR	homeostasis model assessment – estimated insulin resistance
IWRS	interactive web response system
LFC	liver fat content
MedDRA	Medical Dictionary for Regulatory Activities
MRI-PDF	magnetic resonance imaging – estimated proton density fat fraction
NASH	nonalcoholic steatohepatitis
PP	per protocol
PT	preferred term
SAE	serious adverse event
SD	standard deviation
SOC	system organ classification
T2DM	type 2 diabetes mellitus
TEAE	treatment emergent adverse events
WHO	World Health Organization

2. **OBJECTIVES**

Primary Objective:

The objective of this study is to evaluate the effects of HTD1801 on liver fat content (LFC) in adults with NASH and T2DM.

Secondary Objective:

The secondary objectives are to evaluate the following:

- The effects of HTD1801 on hemoglobin A1c (HbA1c) and glucose metabolism
- The effects of HTD1801 on lipid profile
- The effects of HTD1801 on liver-associated enzymes
- The effects of HTD1801 on biomarkers of liver inflammation and fibrosis
- The effects of HTD1801 on bile acid homeostasis
- The safety and tolerability of HTD1801

3. **GENERAL STATISTICAL CONSIDERATIONS**

3.1. **SAMPLE SIZE AND POWER**

An absolute change in LFC of 5% as measured by magnetic resonance imaging-estimated proton density fat fraction (MRI-PDFF) has been reported to be the minimal clinically significant difference between active treatment and placebo that correlates with histological improvement in NASH (Loomba et al., 2015, Patel et al., 2015). Furthermore, Harrison and colleagues reported a pooled standard deviation of 6.3% for changes from Baseline in LFC (Harrison et al., 2018). Based on this standard deviation, 35 subjects in each treatment group will provide 90% power to show a difference of 5 percentage points between any 2 treatment groups at the 5% level of significance. To allow for a dropout rate of 10%, 39 subjects will be randomized to each of the 3 treatment groups. Due to the exploratory nature of this study, enrollment may be stopped early when sufficient information has been gathered to evaluate the effects of HTD1801 on LFC.

An interim analysis will be conducted after a minimum of 51 subjects complete the assessment of the primary efficacy endpoint to assess sample size assumptions and futility through conditional power.

3.2. **RANDOMIZATION AND MASKING**

This is a multicenter, randomized, double-blind study. Subjects will be centrally randomized via an interactive web response system (IWRS) in a 1:1:1 ratio to one of 3 groups:

HTD1801 500 mg BID

HTD1801 1000 mg BID

Placebo BID

In addition to the subject ID number, subjects will be assigned a randomization number, as well as a kit ID number corresponding to a pre-packaged and numbered study drug kit. The randomization schedule was prepared by a non-study statistician using PharPoint standard operating procedure BIO002.

All subjects and study personnel, except for the unblinded statistician, the IWRS vendor and the study drug packaging supplier, will remain blinded to the treatment administered throughout the study. All study drugs will be provided in matching white tablets, 4 tablets to a pouch, 2 pouches to be administered each day.

3.3. HANDLING OF DATA

3.3.1. Strata and Covariates

Selected efficacy analyses will include Baseline LFC and Baseline ALT as covariates.

3.3.2. Examination of Subject Subsets

Selected efficacy analyses will be presented by Baseline HbA1c group ($< 7\%$ vs. $\geq 7\%$).

3.3.3. Multiple Testing and Comparisons

All analyses will be conducted without adjustments for multiple comparisons.

3.3.4. Missing Data and Outliers

Every effort will be made to obtain required data at each scheduled evaluation from all subjects who have been treated. For subjects who do not complete the 18-week evaluation, endpoints that will only be measured at Week 18 or the Early Termination (ET) visit (i.e., LFC, HOMA-IR, Pro-C3, ELF) will have the value at the ET visit carried forward for the missing Week 18 visit.

For all non-LFC secondary endpoints measured at at least one post-baseline timepoint other than Week 18/ET, missing Week 18 values will be imputed using a multiple imputation procedure for all subjects with an available measurement prior to Week 18. Multiple imputation relies on the assumption that the data are missing at random. This method of imputation produces unbiased estimators of the mean and standard error, and, as such, is preferred over single imputation methods. For this method, the procedure requires production of multiple datasets containing plausible values for each missing value. These plausible values are generated using available auxiliary information (site, treatment, baseline assessment value, baseline LFC, and baseline ALT).

Using a set of values rather than a single value better accounts for the uncertainty about the value being imputed. For this imputation, the Markov chain method will be used. SAS PROC MI will be used to generate 10 possible imputed datasets.

For each variable that has imputations performed, the following steps will be followed:

1. Missing values will be imputed using PROC MI. This will result in 10 datasets per variable.
2. Efficacy endpoints will be derived from the appropriate set of 10 datasets produced by PROC MI using the imputed values.
3. Each efficacy endpoint will be analysed 10 times (once per source dataset) using the appropriate statistical model for that endpoint.
4. For each endpoint, the results from the analysis from each of the 10 datasets will be combined using PROC MIANALYZE to produce an inferential result for the parameter of interest.

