9.2.2 Analysis Datasets

The efficacy dataset will consist of all randomized subjects who meet the following conditions:

- For analysis of the primary efficacy endpoint, randomized subjects who complete at least 80 days of study drug dosing and have a Week 18 (or ET) visit MRI-PDFF assessment.
- For analysis of the secondary efficacy endpoints, randomized subjects who receive at least one dose of study drug and have at least one post-dose assessment.

The safety dataset will include all randomized subjects who receive at least one dose of study drug.

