4.2. MODIFIED EFFICACY SET

The Modified Efficacy set will consist of all randomized subjects who receive at least one dose of study drug and who have at least one post-dose MRI-PDFP assessment. Subjects in this set will be analyzed according to the treatment to which they were randomized. This set will be utilized for analyses of secondary endpoints, as well as select analyses of the primary endpoint.

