10. PROPOSED TABLES, LISTINGS, AND FIGURES

Summary Tables

Accountability and Baseline Characteristics

- 14.1.1.1 Subject Disposition – All Randomized Subjects
- 14.1.1.2 Protocol Deviations – All Randomized Subjects
- 14.1.2 Demographics and Baseline Characteristics – Safety Set
- 14.1.3 Extent of Exposure and Treatment Compliance – Safety Set
- 14.1.4 Concomitant Medications by ATC Classification and Preferred Term- Safety Set

Efficacy

- 14.2.1.1 Liver Fat Content by Time Point – Efficacy Set
- 14.2.1.2 Liver Fat Content by Time Point – Modified Efficacy Set
- 14.2.1.3 Liver Fat Content by Time Point – Per Protocol Set
- 14.2.2.1 Changes in Fasting Glucose from Baseline to Week 18 – Modified Efficacy Set
- 14.2.2.2 Changes in HbA1c from Baseline to Week 18 – Modified Efficacy Set
- 14.2.2.3 Changes in HOMA-IR from Baseline to Week 18 – Modified Efficacy Set
- 14.2.2.4 Changes in LDL-c from Baseline to Week 18 – Modified Efficacy Set
- 14.2.2.5 Changes in Serum Triglycerides from Baseline to Week 18 – Modified Efficacy Set
- 14.2.2.6 Changes in HDL-c from Baseline to Week 18 – Modified Efficacy Set
- 14.2.2.7 Changes in AST from Baseline to Week 18 – Modified Efficacy Set
- 14.2.2.8 Changes in ALT from Baseline to Week 18 – Modified Efficacy Set
- 14.2.2.9 Changes in Pro-C3 from Baseline to Week 18 – Modified Efficacy Set
- 14.2.2.10 Changes in ELF Score and Components from Baseline to Week 18 – Modified Efficacy Set
- 14.2.2.11.1 Changes in Total Bile Acids from Baseline to Week 18 – Modified Efficacy Set
- 14.2.2.11.2 Changes in Total Primary Bile Acids from Baseline to Week 18 – Modified Efficacy Set
- 14.2.2.11.3 Changes in Total Secondary Bile Acids from Baseline to Week 18 - Modified Efficacy Set
- 14.2.2.11.4 Changes in Total Ursodeoxycholic Acid from Baseline to Week 18 – Modified Efficacy Set
- 14.2.2.12 Changes in C4 from Baseline to Week 18 – Modified Efficacy Set
- 14.2.2.13 Changes in FGF19 from Baseline to Week 18 – Modified Efficacy Set
- 14.2.2.14 Changes in GGT from Baseline to Week 18 – Modified Efficacy Set

Safety

- 14.3.1.1 Overall Summary of Treatment-Emergent Adverse Events– Safety Set
- 14.3.1.2 Treatment-Emergent Adverse Events by System Organ Class, Preferred Term, and Greatest Severity – Safety Set
- 14.3.1.3 Treatment-Emergent Adverse Events Related to Study Drug by System Organ

- Class and Preferred Term – Safety Set

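### The imputation model for Week 18 laboratory values names no on-treatment predictor, and the SAP's secondary set drops the patients that imputation is meant to keep

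*SAP*

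**What the plan says.** **Imputation.** For non-LFC secondary endpoints with a post-baseline visit other than Week 18/ET, SAP 3.3.4 states that "missing Week 18 values will be imputed using a multiple imputation procedure for all subjects with an available measurement prior to Week 18". It then names the predictors: "These plausible values are generated using available auxiliary information (site, treatment, baseline assessment value, baseline LFC, and baseline ALT". The method is a Markov chain procedure with 10 datasets.

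**Values available.** Under SAP 1.2, the chemistry panel at Weeks 2, 6 and 14 "only includes testing of ALP, ALT, AST, GGT, total bilirubin, direct bilirubin, and fasting glucose", and the full panel is drawn at Week 10. ALT, AST, GGT and glucose therefore have four on-treatment values before Week 18. HbA1c, lipids and bile acids have one, at Week 10.

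**Analysis set.** The SAP 4.2 Modified Efficacy set takes dosed subjects "who have at least one post-dose MRI-PDFP assessment", and "This set will be utilized for analyses of secondary endpoints, as well as select analyses of the primary endpoint". SAP 10 assigns the laboratory tables to it, for example "Changes in HbA1c from Baseline to Week 18 – Modified Efficacy Set". SAP 3.3.4 counts LFC among the "endpoints that will only be measured at Week 18 or the Early Termination (ET) visit (i.e., LFC, HOMA-IR, Pro-C3, ELF", so no post-dose MRI is scheduled earlier. For secondary endpoints, Protocol 9.2.2 asks only that randomized subjects "receive at least one dose of study drug and have at least one post-dose assessment".

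**ET values.** Protocol 9.2.3.2 uses the ET value for dropouts in every listed secondary endpoint. Protocol 9.2.4 uses it for LFC only and imputes the rest. SAP 3.3.4 carries it forward for LFC, HOMA-IR, Pro-C3 and ELF. SAP 3.3.6, which deals with summary displays, maps ET visits to Week 18.

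**The concern.** An earlier measurement admits a subject to imputation but, on the listed predictors, does not inform the imputed value. Treatment and baseline value are already in the ANCOVA of SAP 5.2.5. Drawing missing values from them, with baseline LFC, baseline ALT and site added, gives dropouts the completers' average for their arm and baseline. The missing-at-random assumption must then hold given baseline data alone, although data that would make it easier to meet are already collected. The HbA1c run without imputation, planned in SAP 5.2.5, is for the same reason a weak check.

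The set rule compounds this. A patient who leaves after Week 10 with HbA1c and ALT on file, but has no ET MRI, is dropped from the laboratory analyses rather than imputed. If dropout depends on response and differs between arms in rate or mechanism, the treatment difference is biased. The endpoints include HbA1c and glucose, which belong to the first-listed secondary objective. HOMA-IR, Pro-C3 and ELF have no intermediate value, so the predictor list does not affect them. The ET conflict and the set rule do.

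**Working it through.** **The plan's own figures.** With a difference of 5, SD 6.3, two-sided 5% and 90% power, the normal approximation gives 34 per group. The t-test gives power 0.897 at 34 and 0.905 at 35, so 35 reproduces. 35/0.90 = 38.9, hence 39 per group and 117 in total. Planned dropout is 39 × 0.10 = 3.9, about 4 per arm, or 117 − 105 = 12 overall.

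**Who is left to impute.** Everyone in the SAP 4.2 set had an MRI at Week 18 or ET, and Protocol 5.1.5 repeats the Week 18 laboratory tests at ET. Of about 4 dropouts per arm:
- If half have an ET MRI, about 2 are excluded and about 2 have ET laboratory values.
- If 80% have one, the split is about 0.8 and 3.1.

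If ET counts as Week 18, almost nothing is left to impute. If it does not, observed ET values are replaced by draws from baseline.

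**Bias with the listed predictors, ET not used.** The documents give no correlations or arm-specific dropout rates, so these are assumptions:
- baseline/Week 18 correlation 0.6, so the Week 18 SD given baseline is s = √(1 − 0.6²) = 0.8;
- on-treatment/Week 18 correlation given baseline r = 0.4 to 0.8;
- dropout/on-treatment response correlation c = 0.45 to 0.70, with normally distributed dropout propensity.

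In an arm with dropout p, the completers' baseline-adjusted mean shifts by s·r·c·k(p), where k(p) = φ(z)/(1 − p) and z is the upper-p normal quantile. Values imputed from baseline and arm inherit the same shift. The bias in the difference is therefore s·r·c·[k(active) − k(placebo)].

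- s·r·c runs from 0.8 × 0.4 × 0.45 = 0.144 to 0.8 × 0.8 × 0.70 = 0.448.
- k(5%) = 0.1031/0.95 = 0.1086; k(10%) = 0.1755/0.90 = 0.1950; k(15%) = 0.2332/0.85 = 0.2743; k(20%) = 0.2800/0.80 = 0.3500.

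| Dropout, active/placebo | Difference in k | Bias by formula (SD) | Simulation (SD) |
|---|---|---|---|
| 15%/5% | 0.1657 | 0.024–0.074 | 0.027–0.073 |
| 20%/5% | 0.2414 | 0.035–0.108 | 0.037–0.108 |
| 5%/15% | −0.1657 | 0.024–0.074, opposite sign | 0.021–0.075, opposite sign |
| 10%/10%, same mechanism | 0 | 0 | within 0.004 |
| 10%/10%, response-related in one arm only | 0.1950 | 0.028–0.087 | 0.03–0.09 |

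The simulations are large-sample, with error of about 0.003 SD. At 15%/5% and 20%/5%, completers-only ANCOVA gave the same ranges as the listed predictors. In a finite-sample check (39 per arm, 10 imputations) the two estimates correlated 0.990 to 0.996.

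**After the change.** On the protocol set, with the endpoint's on-treatment value in the model and every dropout having one, the bias is within 0.003 SD of zero. Changing only the predictors, and keeping the SAP 4.2 set, leaves 0.01 to 0.05 SD with 50% ET MRI capture and 0.005 to 0.017 SD with 80%, at 15–20% against 5% dropout. Counting ET as Week 18 on that set gives the same, if an ET value is taken to equal the Week 18 value.

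**Week 10 endpoints.** A dropout before Week 10 has no on-treatment HbA1c, lipid or bile acid value and, reading the SAP's earlier measurement as post-baseline, is not imputed. If a fraction f of dropouts leave that early, the remaining shift per arm is s·r·c·f·φ(z)/(1 − f·p). With f = 0.5 at 20%/5%: 0.1400/0.90 − 0.0516/0.975 = 0.1556 − 0.0529 = 0.1027. Multiplied by 0.144 and 0.448, this gives 0.015 and 0.046; simulation gave about 0.02 to 0.04 SD.

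**Yardstick.** The standard error of a difference is about 0.8 × √(2/35) = 0.19 SD.

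**The case against.** The strongest reply is that the SAP is silent rather than wrong. It calls the list auxiliary information, admits only subjects with an earlier measurement, and uses a method well suited to a model with earlier visits. A reader might infer that the SAP forbids on-treatment predictors. It does not, and they may have been intended. What stands is that the list is explicit and a programmer following it would leave them out.

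Second, the ET passages have a coherent reading: SAP 3.3.4 speaks of Week 18/ET as one timepoint, SAP 3.3.6 maps ET to Week 18, and Protocol 9.2.3.2 uses ET for dropouts. Little is then imputed within the SAP 4.2 set, and the predictor list hardly matters there. This is a fair point, and it makes the predictor change useful mainly once the set is aligned with the protocol. It does not remove the conflict between Protocol 9.2.3.2 and 9.2.4, nor the exclusion of dropouts without an MRI.

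Third, size. The only dropout rate in the documents is 10%, with about four dropouts per arm; the unequal rates are assumed. The study is proof-of-concept and its secondary tests are not adjusted for multiplicity. All of this is right and limits the weight of the point.

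**Conclusion.** The point holds as a gap in specification plus a discrepancy in the analysis set, and is worth correcting before programming. With the listed predictors and ET not used, the bias is about 0.02 to 0.11 SD when dropout rates differ by arm, and about 0.03 to 0.09 SD at equal 10% dropout if only one arm's dropout depends on response. It is about zero only when rate and mechanism are the same in both arms. Even the largest value is below the standard error of 0.19 SD, and every figure rests on the assumed correlations and dropout patterns.

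Several stronger conclusions are tempting and not supported:
- **That the plan favours the active arms.** The direction depends on which arm loses more patients and on whether poor or good responders leave.
- **That the primary endpoint is affected.** LFC is not multiply imputed.
- **That the SAP's statement on unbiasedness is an error.** It is conditional on missing at random.
- **That the same sizes apply to ALT normalization.** Only continuous endpoints were simulated.
- **That the fix removes all bias.** For HbA1c, lipids and total bile acid about 0.02 to 0.04 SD remains at 20%/5% if half of dropouts leave before Week 10.

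**What to change.** - **SAP 3.3.4:** keep the listed predictors and add each endpoint's own scheduled post-baseline values: Weeks 2, 6, 10 and 14 for ALT, AST and glucose (and GGT, if imputed); Week 10 for HbA1c, lipids and total bile acid. State whether GGT and AST normalization, listed in SAP 5.2.4 without a stated analysis in 5.2.5, are imputed.
- **SAP 4.2 and 10:** use the Protocol 9.2.2 secondary set for the laboratory endpoints, so that dropouts with on-treatment values but no MRI are imputed. Keep the MRI requirement for LFC.
- **ET rule:** state for each endpoint whether an ET value counts as Week 18 before imputation, and reconcile Protocol 9.2.3.2 and 9.2.4 with SAP 3.3.4 and 3.3.6.

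The cost is SAP wording and a few lines of code, with no new data. No gain in precision is claimed. Report by arm how many dropouts left before Week 10, since the change cannot recover their HbA1c, lipid and bile acid values.
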